6.2.7 Recurrence Disease Free Survival

Recurrence disease free survival will be defined as the time from surgery until patient develops recurrence.

6.3 Safety/tolerability

Analyses will be performed for all patients having received at least one dose of study drug. The study will use the CTCAE version 5.0 for reporting of non-hematologic adverse events (<http://ctep.cancer.gov/reporting/ctc.html>) and modified criteria for hematologic adverse events (Appendix #/letter).

7.0 ADVERSE EVENTS

Adverse event (AE) monitoring and reporting is a routine part of every clinical trial. The investigator will use CTCAE v 5.0 to assign AE severity grades. Investigators are responsible for monitoring the safety of patients who have entered this study and for alerting Eli Lilly Pharmaceuticals to any event that seems unusual, even if this event may be considered an unanticipated benefit to the patient.

The investigator is responsible for the appropriate medical care of patients during the study.

The investigator remains responsible for following, through an appropriate health care option, AEs that are serious or otherwise medically important, considered related to the investigational product or the study, or that caused the patient to discontinue the investigational product before completing the study. The patient should be followed until the event resolves, stabilizes with appropriate diagnostic evaluation, or is otherwise explained. The frequency of follow-up evaluations of the AE is left to the discretion of the investigator.

Lack of drug effect is not an AE in clinical trials, because the purpose of the clinical trial is to establish drug effect.

After the ICF is signed, study site personnel will record via OnCore eCRF the occurrence and nature of each patient's preexisting conditions, including clinically significant signs and symptoms of the disease under treatment in the study. In addition, site personnel will record any change in the condition(s) and any new conditions as AEs. Investigators should record their assessment of the potential relatedness of each AE to protocol procedure, investigational product, via OnCore eCRF.

The investigator will interpret and document whether or not an AE has a reasonable possibility of being related to study treatment taking into account the disease, concomitant treatment or pathologies.

A "reasonable possibility" means that there is a cause and effect relationship between the investigational product, study device and/or study procedure and the AE.

Planned surgeries and nonsurgical interventions should not be reported as AEs unless the underlying medical condition has worsened during the course of the study.

If a patient's investigational product is discontinued as a result of an AE, study site personnel must report this to Eli Lilly Pharmaceuticals via Eli Lilly's IIR Portal for Trial Management or via fax, clarifying if possible, the circumstances leading to any dosage modifications, or discontinuations of treatment.

CONFIDENTIAL

This material is the property of the [UC Irvine Chao Family Comprehensive Cancer Center](#). Do not disclose or use except as authorized in writing by the study sponsor.

7.1 Definitions

7.1.1 Event Definition

Adverse event (AE) - An adverse event is any untoward medical experience or change of an existing condition that occurs during or after treatment, whether or not it is considered to be related to the protocol intervention.

Unexpected Adverse Event [Modified from the definition of unexpected adverse drug experience in FDA regulations at 21 CFR 312.32 (a)] – An adverse event is unexpected if it is not listed in the investigator's brochure and/or package insert; is not listed at the specificity or severity that has been observed; is not consistent with the risk information described in the protocol and/or consent; is not an expected natural progression of any underlying disease, disorder, condition, or predisposed risk factor of the research participant experiencing the adverse event.

Expected Adverse Event - Any event that does not meet the criteria for an unexpected event OR is an expected natural progression of any underlying disease, disorder, condition, or predisposed risk factor of the research participant experiencing the adverse event.

Serious Adverse Event (SAE) [21 CFR 312.32] - Defined as any expected or unexpected adverse event that result in any of the following outcomes:

- Death
- Is life-threatening experiences (places the subject at immediate risk of death from the event as it occurred)
- Unplanned hospitalization equal or greater than 24 hours)) or prolongation of existing hospitalization
- A persistent or significant disability/incapacity
- A congenital anomaly/birth defect
- Any other adverse event that, based upon appropriate medical judgment, may jeopardize the subject's health and may require medical or surgical intervention to prevent one of the outcomes listed above (examples of such events include allergic bronchospasm requiring intensive treatment in the emergency room or at home, blood dyscrasias or convulsions that do not result in inpatient hospitalization, or the development of drug dependency or drug abuse).

Unanticipated problem (UP) - Any incident, experience or outcome that meets all three of the following criteria:

1. Unexpected (in term nature, severity, or frequency) given the following: a) the research procedures described in the protocol-related documents such as the IRB approved research protocol, informed consent document or Investigator Brochure (IB); and b) the characteristics of the subject population being studied; **AND**
2. Related or possibly related to participation in the research (possibly related means there is a reasonable possibility that the incident, experience, or outcomes may have been caused by the drugs, devices or procedures involved in the research); **AND**

CONFIDENTIAL

This material is the property of the [UC Irvine Chao Family Comprehensive Cancer Center](#). Do not disclose or use except as authorized in writing by the study sponsor.

3. Suggests that the research places subjects or others at greater risk of harm (including physical, psychological, economic, or social harm) than previously known or recognized.

Protocol Violation- A protocol violation is an accidental or unintentional change to or noncompliance with the IRB-approved protocol that increases risk or decreases benefit and/or affects the subject's rights, safety, welfare, and/or the integrity of the data. Examples of incidents that may be considered violations include: enrolling a participant who does not meet the inclusion criteria; obtaining verbal consent before the initiation of study procedures when the IRB requires signed, written informed consent; and failure to collect screening labs before initiation of study procedures [Reference: Policy #57 UCI HRPP Policy and Procedure Glossary].

Protocol Deviation- A protocol deviation is an accidental or unintentional change to the research protocol that does not increase risk or decrease benefit or have a significant effect on the participant's rights, safety or welfare, or on the integrity of the data. Deviations may result from the action of the participant, researcher, or staff. Examples: a rescheduled study visit, an omitted routine safety lab for a participant with previously normal values; or failure to collect an ancillary self-report questionnaire data (e.g., quality of life) [Reference: Policy #57 UCI HRPP Policy and Procedure Glossary].

Characteristics and Severity of Adverse Events

All non-hematologic adverse events will be graded according to the NCI Common Terminology Criteria for Adverse Events (CTCAE) version 5.0. The CTCAE v5 is available at https://ctep.cancer.gov/protocoldevelopment/electronic_applications/docs/CTCAE_v5_Quick_Reference_5x7.pdf

If no CTCAE grading is available, the severity of an AE is graded as follows:

Mild (grade 1): the event causes discomfort without disruption of normal daily activities.

Moderate (grade 2): the event causes discomfort that affects normal daily activities.

Severe (grade 3): the event makes the patient unable to perform normal daily activities or significantly affects his/her clinical status.

CONFIDENTIAL

This material is the property of the [UC Irvine Chao Family Comprehensive Cancer Center](#). Do not disclose or use except as authorized in writing by the study sponsor.

7.1.2 Characteristics and Severity of Adverse Events

All non-hematologic adverse events will be graded according to the NCI Common Terminology Criteria for Adverse Events (CTCAE) version 5.0. The CTCAE v5 is available at:
https://ctep.cancer.gov/protocoldevelopment/electronic_applications/docs/CTCAE_v5_Quick_Reference_5x7.pdf

If no CTCAE grading is available, the severity of an AE is graded as follows:

Mild (grade 1): the event causes discomfort without disruption of normal daily activities.

Moderate (grade 2): the event causes discomfort that affects normal daily activities.

Severe (grade 3): the event makes the patient unable to perform normal daily activities or significantly affects his/her clinical status.

Life-threatening (grade 4): the patient was at risk of death at the time of the event.

Fatal (grade 5): the event caused death.

Attribution of the AE:

- Definite – The AE is clearly related to the study treatment.
- Probable – The AE is likely related to the study treatment.
- Possible – The AE may be related to the study treatment.
- Unlikely – The AE is doubtfully related to the study treatment.
- Unrelated – The AE is clearly NOT related to the study treatment.

7.1.3 Serious Adverse Events

A “serious” adverse event is defined in regulatory terminology as any untoward medical occurrence that:

7.1.3.1 Results in death.

If death results from (progression of) the disease, the disease should be reported as event (SAE) itself.

7.1.3.2 Is life-threatening.

(the patient was at risk of death at the time of the event; it does not refer to an event that hypothetically might have caused death if it were more severe).

CONFIDENTIAL

This material is the property of the [UC Irvine Chao Family Comprehensive Cancer Center](#). Do not disclose or use except as authorized in writing by the study sponsor.

- 7.1.3.3 Requires in-patient hospitalization or prolongation of existing hospitalization for ≥ 24 hours.
- 7.1.3.4 Results in persistent or significant disability or incapacity.
- 7.1.3.5 Is a congenital anomaly/birth defect
- 7.1.3.6 Is an important medical event
 - Any event that does not meet the above criteria, but that in the judgment of the investigator jeopardizes the patient, may be considered for reporting as a serious adverse event. The event may require medical or surgical intervention to prevent one of the outcomes listed in the definition of "Serious Adverse Event".
For example: allergic bronchospasm requiring intensive treatment in an emergency room or at home; convulsions that may not result in hospitalization; development of drug abuse or drug dependency.

7.2 Steps to Determine If an Adverse Event Requires Expedited Reporting

Step 1: Identify the type of adverse event using the NCI Common Terminology Criteria for Adverse Events (CTCAE v5).

Step 2: Grade the adverse event using the NCI CTCAE v5.

Step 3: Determine whether the adverse event is related to the protocol therapy
Attribution categories are as per section 7.3.2:

Note: This includes all events that occur within 30 days of the last dose of protocol treatment. Any event that occurs more than 30 days after the last dose of treatment and is attributed (possibly, probably, or definitely) to the agent(s) must also be reported accordingly.

Step 4: Determine the prior experience of the adverse event.

Expected events are those that have been previously identified as resulting from administration of the agent. An adverse event is considered unexpected, for expedited reporting purposes only, when either the type of event or the severity of the event is not listed in:

1. the current known adverse events listed in the Agent Information Section of this protocol;
2. the drug package insert;
3. the current Investigator's Brochure

CONFIDENTIAL

This material is the property of the [UC Irvine Chao Family Comprehensive Cancer Center](#). Do not disclose or use except as authorized in writing by the study sponsor.

7.3 Reporting Requirements for Adverse Events

Adverse events, serious adverse events, deviations, violations, and unanticipated problems must be entered into the clinical trial management system (CTMS), OnCore, and must also be reported to the following entities according to the timelines mentioned in the chart below. Serious adverse events collection will start at the time patient signs consent until 30 days after the end of treatment. Adverse events will be collected from the time the research patient begins treatment until 30 days after the end of treatment. All adverse events/serious adverse events should be followed until resolution or stabilization.

Event Type	Coordinating Center/Medical Monitor	UCI IRB	Eli Lilly Pharmaceuticals*	CFCCC DSMB
Unanticipated Problem (UP)	Within 24 hours from date the site is aware of the event, the site should enter this information into OnCore. An email notification should also be sent via email to [contact] and [contact] .	Within 5 business days submit an Unanticipated Problem Report (UP) . Current policy can be found here .	Within 15 business days of learning of the event. Submit an SAE Form to Eli Lilly's IIR Portal for Trial Management (https://www.lillyinvestigatorresearch.com) OR via [contact]). Serious adverse events should be reported to Lilly using a CIOMS Form or other form acceptable to Lilly.	Within 5 days from date PI is aware of the event. This information must be reported into OnCore.
AEs and SAEs (non-Unanticipated Problem)	Please refer to section 7.4 for reporting timeframes on AEs and SAEs.	N/A	Only SAEs are required to be reported within 15 business days of learning of the event. Please see section 7.6 below for additional reporting for SAEs that are non-UPs.	Please refer to section 7.4 for clarification on reporting timeframes for AEs and SAEs.
Non-compliance	N/A	N/A	N/A	Please refer to section 7.4 for reportable deviations/violations.

CONFIDENTIAL

This material is the property of the [UC Irvine Chao Family Comprehensive Cancer Center](#). Do not disclose or use except as authorized in writing by the study sponsor.

Serious or continuing non-compliance	Within 24 hours via email to [contact] and [contact]	Within 5 business days submit a New Information Report	N/A	Within 5 days from date PI is aware of the event.
Prospective/Planned Deviations	At least 5 business days prior to the event via email to [contact] and [contact] for approval.	At least 48 hours prior to date the request is needed by. Submit a Prospective Deviation Request form	N/A	At the time of progress review as aggregate reports.

*Patients who become pregnant must be reported along same timelines as SAE. Please reference section 7.5 below in regards to additional safety information required to be reported to Eli Lilly Pharmaceuticals for subjects who become pregnant.

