1.4 Rationale

Neoadjuvant Endocrine Therapy:

Neo-adjuvant chemotherapy (NACT) refers to systemic treatment of breast cancer prior to definite surgical treatment. While all systemic therapy given for non-metastatic invasive breast cancer is intended to reduce the risk of distant recurrence, the purpose of administering it neoadjuvantly is to downstage the tumor, allow for less extensive surgery, improve cosmetic outcomes and reduce postoperative complications (1). By reducing the size of the primary tumor, preoperative therapy also allows for higher rate of breast conserving surgery. Achieving a complete pathologic response to Neo-Adjuvant chemotherapy has prognostic implications in patients with breast cancer (2, 3) and failure to achieve a complete pathologic response are associated with a high risk of local relapse.

Unlike Her-2+ and Triple negative breast cancers, HR+ breast cancers are less likely to respond to NACT (4-8). Chemotherapy can shrink HR+ tumors and facilitate better surgical outcomes, but is less likely to achieve a complete pCR in HR+ cancers, especially luminal A cancers than for more proliferative histology (9, 10). While historically neoadjuvant endocrine therapy (NET) has been reserved for patients with substantial comorbid health problems who would not tolerate chemotherapy, it is coming to be seen as a viable alternative for other patients, especially those with strong HR+ tumors that are strongly ER+. Tumors that are more likely to respond to NET have strong

CONFIDENTIAL

This material is the property of the [UC Irvine Chao Family Comprehensive Cancer Center](#). Do not disclose or use except as authorized in writing by the study sponsor.

HR expression ($\geq 50\%$ ER+ or an Allred score of 7 or 8) and a low proliferative index (Ki 67 < 10 or 15 %).

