The standard of care options for Post-menopausal patient who develop localized or locally advanced recurrent HR+ Breast cancer while on adjuvant endocrine therapy remains to be surgical resection. The treatment depends on the type of local treatment they received at the initial diagnosis. Recurrence can happen after a lumpectomy and radiation or following mastectomy. Mastectomy is the surgical standard of care for most patients with a local recurrence following breast conserving surgery and radiation. Surgery in the form of wide local excision is recommended for post mastectomy chest wall recurrence. The role of radiation in the management of localized recurrence also depends upon if patients received adjuvant radiation at the initial diagnosis. Surgery and radiation in recurrent HR + breast cancer only address local control. Patients with recurrent breast cancer are at risk of developing metastatic breast cancer, have microscopic metastasis and many have evidence of endocrine resistance. Furthermore, extensive loco-regional recurrence is not amenable to surgical resection alone. Surgery and radiation does not address endocrine resistance nor does it treat microscopic metastasis. Hence, addressing endocrine resistance as well as adopting a targeted Neo-Adjuvant approach based on patient's tumor profiling and then treating them with the Abemaciclib and Fulvestrant to downstage the tumor, limit chemotherapy induced toxicity is the next logical step in the management of patients. These patients often land up getting Neo-Adjuvant chemotherapy. Few achieve a complete pathologic response and many are subjected to severe peri-operative complications. Hence, there continues to be an unmet medical need to develop alternate therapies that are less toxic and provide better outcomes. Neoadjuvant endocrine therapy can be an alternative option to chemotherapy in Hormone Receptor positive (HR+) tumors, particularly for postmenopausal women. Unlike in premenopausal women, available data suggest that NET is associated with similar response rates and rates of breast- conserving surgery (BCS) as NACT with lower toxicity, although survival data with NET are not yet available (11-15).

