4.1.2 Supportive Care Guidelines

Necessary supportive measures for optimal medical care will be given throughout the study including antidiarrheal, blood components etc. Additional care will be administered as indicated by the treating physician and the subject's medical need. All the concomitant medications and supportive therapy administered during the 30 days prior to the first dose until 30 days after the last dose must be recorded in OnCore eCRF.

4.2 **Toxicities and Dosing Delays/Dose Modifications**

Any patient who receives treatment on this protocol will be evaluable for toxicity. Each patient will be assessed for the development of toxicity according to the Time and Events table (Section 5.4). Toxicity will be assessed according to the NCI Common Toxicity Criteria for Adverse Events (CTCAE), version 5.0. Dose adjustments should be made according to the system showing the greatest degree of toxicity.

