5.5 Time and Events Table

If baseline evaluations are conducted within 1 week prior to administration of protocol therapy, those assessments do not need to be repeated. Scans must be done \leq 4 weeks prior to the start of therapy. In the event that the patient's condition is deteriorating, laboratory evaluations should be repeated within 48 hours prior to initiation of the next cycle of therapy.

	Baseline/Screening	Treatment Phase		Post-discontinuation		
	-28 to -1 days	Cycle 1	Subsequent cycles	End of Treatment	Surgery	Follow-up

CONFIDENTIAL

This material is the property of the [UC Irvine Chao Family Comprehensive Cancer Center](#). Do not disclose or use except as authorized in writing by the study sponsor.

		D1 (-3d)	D15 (±3d)	D1 (-3d)	Within 30 days of last dose prior to surgery		Every 6 months (±14d)
Assessment							
Informed Consent	X						
History and PE	X	X		X	X		
Vital Signs	X	X	X	X	X		
Baseline medical and oncology history	X						
Concomitant Medications	X	X		X	X		
ECOG Performance Status	X	X		X	X		X
Adverse Events		X		X	X		
Tumor Measurements	X						
CT CAP or CT chest/MRI Abd/Pelvis ¹	X						
MRI Breast	X			X Every 12 weeks (±7d) after first dose until maximum response or progression, whichever occurs first			
CBC w/diff	X	X	X	X	X		
CMP	X	X	X	X	X		
Postmenopausal Confirmation	X						
ctDNA (correlative study)	X			X ²			X
Biopsy ³					X		
Tissue Submission	X				X	X	
Administer Abemaciclib		X	X	X			
Administer Fulvestrant		X	X	X			
Study Drug Accountability				X	X		

¹ CT Chest, abdomen and pelvis with contrast or CT chest/MRI Abdomen, Pelvis is required at screening to rule out metastasis

² Every 3 months during treatment

CONFIDENTIAL

This material is the property of the [UC Irvine Chao Family Comprehensive Cancer Center](#). Do not disclose or use except as authorized in writing by the study sponsor.

³ A fresh biopsy at time of progression is mandatory if clinically feasible.

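### Adverse event collection is tied to the last dose rather than to surgery, so post-operative harm is captured unevenly; Cycle 1 Day 15 also lacks a scheduled adverse event review

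*Combined protocol and SAP*

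**What the plan says.** Section 7.3 sets both windows by reference to treatment. For all adverse events: "Adverse events will be collected from the time the research patient begins treatment until 30 days after the end of treatment". For serious events only the start differs: "Serious adverse events collection will start at the time patient signs consent until 30 days after the end of treatment".

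Section 4.2 makes the schedule operative: "Each patient will be assessed for the development of toxicity according to the Time and Events table". In that table (5.5) the row reads "Adverse Events X X X". The three marks are at Cycle 1 Day 1, Day 1 of later cycles and End of Treatment. Cycle 1 Day 15, Surgery and Follow-up are blank. The End of Treatment column is headed "Within 30 days of last dose prior to surgery".

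After surgery, Sections 4.6 and 5.4 list only a six-monthly blood sample for ctDNA, to which the table adds ECOG status. The Study Summary and Section 1.4 say that surgery follows treatment but give no interval from last dose to surgery.

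Three other places bear on the point:
- Section 7.2 also requires reporting of events more than 30 days after the last dose if they are possibly, probably or definitely attributed to the agents.
- The footnote in 7.4 says investigators need not actively look for new events after the 30-day period, but should report one they learn of and consider relevant.
- Section 10.2 plans to monitor side effects for the whole duration of the study.

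**The concern.** Treatment in this trial leads to an operation, yet the safety window is defined only by the drug. A post-operative infection, wound problem or bleed is recorded or not depending on how soon the patient reached surgery, and no visit is set to ask about it. Patients whose surgery is late, possibly because of toxicity, have the least post-operative time under observation.

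Safety and toxicity is a secondary objective (2.2.4) and adverse event incidence a secondary endpoint (2.4). The listed effects of abemaciclib in 8.1 include neutropenia, thrombocytopenia and thromboembolism, all relevant around an operation. Section 1.4 raises surgical harm itself: preoperative therapy is meant to "improve cosmetic outcomes and reduce postoperative complications", and of patients now given chemotherapy it says that "many are subjected to severe peri-operative complications". A reader of the results will want to know how these patients fared around surgery, and the data will not be comparable from one patient to the next.

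A smaller matter is Cycle 1 Day 15. The patient is on site for vital signs, blood count, metabolic panel and fulvestrant, but no adverse event review is scheduled.

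**Working it through.** The plan gives no figure to reproduce on this point. The check compares sections and counts days.

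**Where the last check falls.** The End of Treatment column of 5.5 precedes surgery, and the Surgery and Follow-up columns are blank in the adverse event row. Scheduled post-operative adverse event checks are therefore zero for any interval to surgery. Section 5.3.2 gives the same visit as within 30 days of stopping treatment without saying that it precedes surgery, so the two places need reconciling.

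**Post-operative time inside the window.** Let s be the days from last dose to surgery, counting from whichever study drug was given last. The window length is 30 days (7.3). Post-operative days covered = max(0, 30 - s). The documents do not give s, so the values below are assumptions.

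| Assumed s (days) | Post-operative days covered |
|---|---|
| 0 | 30 |
| 7 | 30 - 7 = 23 |
| 14 | 30 - 14 = 16 |
| 21 | 30 - 21 = 9 |
| 28 | 30 - 28 = 2 |
| 30 or more | 0 |

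**What happens after day 30.** Section 7.2 recovers an event only on attribution to the agents, and a wound or infectious complication may well be attributed to the operation. Section 7.4 removes any duty to look and relies on what the investigator happens to learn. Following events to resolution (7.3) applies to events already recorded, not to new ones.

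**Weight of one event.** Section 10.2 plans 32 treated and analyses 29 evaluable patients. One event missed shifts an incidence by 1/32 = 3.1 to 1/29 = 3.4 percentage points.

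**Cycle 1.** Cycle length is 28 days, so Cycle 2 Day 1 is study day 29. With the first review on the day of first dose and no cycle delay, the gap is 29 - 1 = 28 days. Using the 3-day early allowance on Cycle 2 Day 1, it is 29 - 3 - 1 = 25 days.

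**Is the Day 15 blank genuine?** In the same table, vital signs, blood count and metabolic panel carry a Day 15 mark, while history and physical examination do not. Section 5.3.1 also lists adverse events only before each cycle. The blank agrees with the text and is unlikely to come from a damaged table.

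**Consistency.** Monitoring for the whole study (10.2) and collection ending 30 days after treatment (7.3) cannot both describe the plan, since follow-up runs to five years.

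**The case against.** The window is continuous from first dose, so a blank cell does not close it. An event at Day 15 can be recorded then or at the Cycle 2 review, and Section 7.0 tells staff to record any new condition as an adverse event. Laboratory toxicity is measured on Day 15. Patients are told to report loose stools at the first sign (4.2.1) and, in the pill diary, to contact the team about any symptoms. All of this stands. A reader might infer that the trial is blind to early toxicity, and the documents do not support that. What is missing on Day 15 is a structured question, not the ability to record an answer.

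A reader might likewise infer that the trial cannot see harm to surgery at all. That is also too strong. Events inside the 30 days are collectable, late drug-attributed events are reportable (7.2), relevant events that come to light are reportable (7.4), and the reporting table in 7.3 puts no 30-day limit on unanticipated problems. On-treatment toxicity that delays surgery falls inside the window and is followed to resolution. These routes limit the loss, but none is systematic.

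It can also be said that a drug-anchored window fits the stated safety endpoint, and that no objective or endpoint names surgical complications. This is correct. The remarks in 1.4 are background: one describes the general purpose of preoperative therapy and the other describes patients given chemotherapy. They do not make fewer complications a hypothesis of this trial. The objection narrows the point without removing it. Post-operative days still count for some patients and not for others, and 10.2 still says something different from 7.3.

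Finally, the values of s are assumed. They show that coverage can run from 30 days to none. They do not show that events will be lost.

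**Conclusion.** The point holds as one of uneven and unstructured capture. As written, post-operative cover within the window ranges from 30 days to none, depending on an interval that the plan leaves open, and no scheduled review falls after surgery. The zero count of reviews rests on the text of 5.5 alone; the day counts rest on assumed intervals. The gap of 25 to 28 days between cycle 1 reviews assumes no cycle delay and a first review on the day of first dose. It is a secondary matter, because early toxicity remains collectable and is partly measured by other means.

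The primary endpoint is unaffected. What suffers is the interpretation of a secondary safety objective in about 30 patients. The change is worth making because it alters which safety data exist, and post-operative events not asked about at the time are hard to reconstruct.

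**What to change.** 1. In 7.3, collect adverse and serious adverse events until the later of 30 days after last dose or 30 days after surgery. A patient who has no surgery keeps the 30-day rule after last dose. Bring the 30-day wording in 7.2 and 7.4 into line.
2. In 5.5, add an adverse event mark at Cycle 1 Day 15, and one post-operative review by visit or call about 30 days after surgery. A mark in the Surgery column alone would miss wound and infectious events that appear later. Match 5.3 and 5.4 to the table.
3. Record attribution to drug and to surgery separately, so that the two can be tabulated apart. The scale in 7.1.2 refers only to study treatment, although 7.0 also mentions protocol procedures.
4. Tabulate the last-dose-to-surgery interval and any toxicity-related delay. The surgery date is already needed for recurrence disease-free survival (6.2.7), and dosing is tracked through diaries, so the interval can be derived.
5. Reconcile 10.2 with the amended window.

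The cost is more than a change of wording. The schedule holds no study contact between surgery and the first six-monthly follow-up, so each operated patient needs one added contact, at most 32 if 32 are enrolled. There will be more reports, some of them due to surgery rather than drug, which is why attribution must be recorded. The Day 15 review adds no visit.
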